8.7.2 Reporting of death

The report of death should include information such as disease progression and primary or secondary cause of death, if any. An autopsy may be helpful in the assessment of the cause of death, and if an autopsy is performed, the report should include the results of the autopsy.

Deaths must be reported as SAEs to the sponsor or its representative within 24 hours of notification by completing the Serious Adverse Event (SAE) Reporting Form and, in accordance with GCP requirements, the investigator should provide the sponsor and the Ethics Committee with other required information such as autopsy reports and final medical reports. Deaths to be reported include the following two:

- Deaths, whether or not related to the study drug, that occurred from the time the subject signed informed consent until 28 days after the last dose of study drug;
- Deaths that are definitely related or possibly related to the study drug after 28 days after the last dose of study drug (excluding deaths that are not related to the study drug).

8.8 Hospitalization

In general, hospitalization is defined as remaining in an inpatient or emergency ward for observation or treatment (for more than 24 hours). An AE requiring hospitalization is considered a SAE. hospitalization or extended hospitalization for non-medical reasons/convenience, etc. or purely for the purpose of a clinical trial that does not meet the criteria for a medical event cannot be treated as a SAE.

The following hospitalizations are not considered SAEs:

- Staying in an emergency room or other hospital department for no more than 24 hours that does not result in hospitalization (unless considered a medically significant or life-threatening event);
- Hospitalization resulting from elective surgery that was planned prior to the signing of the ICF;
- Hospitalization resulting from a clinical trial protocol requirement;

- Hospitalization resulting from a requirement for a health physical examination (e.g., routine colonoscopy);
- Hospitalization that is not for the purpose of disease treatment and was planned prior to enrollment and needs to be documented;
- Hospitalization not related to a health condition and not requiring medical/surgical intervention (e.g., lack of housing, financial hardship, need for patient care, family reasons);
- Hospitalization for Medicare reimbursement reasons.

Hospitalization for elective surgery, routine clinical procedures, physical examination, admission for observation, or as required by the protocol, but not for AE, is not considered an AE, but is documented in the medical record. If an unanticipated event occurs during this process, it is reported as a "serious" or "non-serious" AE according to routine criteria.

8.9 Pregnancy

Pregnancy in Female Subjects

If a female subject becomes pregnant during the study (from the time of signing informed consent to 28 days after the last dose of study drug), a Pregnancy Report Form should be completed in the same timeframe as the SAE report, reported promptly to the Sponsor, and documented in the eCRF for follow-up of outcomes.

Any occurrence during pregnancy of: spontaneous or induced abortion, birth defects or congenital malformations in the newborn, malformations and anomalies in stillbirths, and serious complications in the mother and newborn should be documented and reported as an SAE.

During the study period, female subjects should discontinue the study drug as soon as they become pregnant and notify the investigator. The investigator should advise the subject and discuss the risks of continuing the pregnancy and possible effects on the fetus, and the subject must withdraw from the study. The investigator should continue to follow subjects until delivery and 30 days after delivery; subjects who fail to deliver will be followed until the end of the pregnancy.

Pregnancy in the Spouse of a Male Subject

If the spouse of a male subject becomes pregnant during the study period (from the time the male subject signs the informed consent to 28 days after the last dose of study drug), a Pregnancy Report Form should be completed in the same timeframe as the SAE report, reported promptly to the Sponsor, and documented in the eCRF for follow-up of the outcome.

Any occurrence during pregnancy of: spontaneous or induced abortion, birth defects or congenital malformations in the newborn, malformations and anomalies in stillbirths, and serious complications in the mother and newborn should be documented and reported as SAEs.

Spouses of male subjects should notify the investigator as soon as they become pregnant during

the study period. The investigator should advise the subject and his/her spouse to discuss the risks of continuing the pregnancy and the possible effects on the fetus; male subjects do not have to withdraw from the study, but the investigator should continue to follow the subject's spouse until delivery and for 30 days after delivery, and in the case of those who fail to deliver, follow up until the end of the pregnancy is required.

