GLP-compliant rat and dog general toxicology/toxicokinetic studies of acute, subchronic (1 and 3 month), and chronic (6-month rat and 9-month dog) duration have been completed. The primary nonclinical toxicology finding at/near clinically relevant exposures were limited to changes in the cardiovascular (BP lowering), hepatic (transaminitis, hypertrophy/increased organ weight, and cholestasis/inflammation), renal (increased BUN, tubular changes, pigmentation, intracellular protein droplets in the epithelium), GI (decreased appetite), and hematopoietic/immunologic (anemia with regeneration and thymic/splenic lymphoid depletion) systems. Safety pharmacology studies [including human ether-à-go go related gene (hERG) (in vitro), central nervous system (rat), respiratory system (rat), and cardiovascular system (dog)] demonstrated a low likelihood of adverse and/or nonmonitorable central nervous system, respiratory, or cardiovascular system effects associated with BN101/belumosudil at clinically relevant exposure levels. Embryo-fetal toxicology (rats and rabbits) fertility (rats) studies showed that BN101/belumosudil demonstrated embryo-fetal toxicity/teratogenicity as well as reduced male fertility (reduced fertility index/sperm concentration/motility and increased abnormal sperm percentage; testes/epididymis (decreased organ weights and degenerative histopathology). Male fertility findings were generally at higher then clinically relevant exposures. In addition, there was no evidence of genotoxicity in the in vitro Bacterial Reverse Mutation Assay, the in vitro Mammalian Chromosome Aberration Test, or the in vivo

Mammalian Erythrocyte Micronucleus Test mutagenicity assay.

For more information about the BN101/belumosudil nonclinical study see the Investigator's Brochure.

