3. STUDY POPULATION

3.1 Inclusion Criteria

Subjects who met all of the following conditions could be enrolled in the study:

- (1) Male or female subjects aged \geq 18 years who have had allogeneic hematopoietic stem cell transplant (allo-HSCT).
- (2) Have persistent cGVHD manifestations and systemic therapy is indicated.
- (3) Previously received at least 1 and not more than 5 lines of systemic therapy for cGVHD².
- (4) Receiving glucocorticoid therapy with a stable dose over the 2 weeks prior to screening; or 4 weeks of prednisone or equivalent doses of other corticosteroids at doses > 0.5 mg/kg/day with persistent manifestations of cGVHD and no improvement; or 2 attempts to reduce the hormone to a lower

Protocol Version 3.0 Version Date: 25 Feb 2022

² The following approach should be used when documenting prior cGVHD treatment:

[•] The initiation of one or more new systemic therapies for cGVHD will be considered the initiation of a new first-line treatment

If multiple medications are intended to be initiated at the same time, the dates of initiation of treatment
with different medications may be spaced up to 4 weeks apart due to schedule delays or medication
availability

Topical medications are not considered a line of therapy

dose level fail and the prednisone dose still needs to be increased to > 0.25 mg/kg/day or an equivalent dose.

- (5) Eastern Cooperative Oncology Group (ECOG) performance status (PS) score: 0 to 1.
- (6) Life expectancy of more than 12 months.

General Criteria

- (7) Female subjects of childbearing potential have a negative serum pregnancy test at screening. Females of childbearing potential are defined as sexually mature females without prior hysterectomy or who have had any evidence of menses in the past 12 months. However, females who have been amenorrheic for 12 or more months are still considered to be of childbearing potential if the amenorrhea is possibly due to prior chemotherapy, anti-estrogens, or ovarian suppression.
- (8) Sexually active females of childbearing potential enrolled in the study must agree to use two forms of accepted methods of contraception during the course of the study and for 3 months after their last dose of study drug. Effective birth control includes:
 - Intra-uterine contraceptive device plus 1 barrier method;
 - Stable doses of hormonal contraception (e.g., oral, injectable, subcutaneously implanted, transdermal) for at least 3 months plus 1 barrier method;

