 - Two barrier methods. Effective barrier methods are male or female condoms, diaphragms, and spermicides (creams or gels that contain a chemical to kill sperm); or
 - A vasectomized partner.
- (9) For male subjects who are sexually active and who are partners of females of childbearing potential: must agree to use 2 recognized methods of contraception during the treatment period and for 3 months after the last dose of study drug (see criterion 8 above).
- (10) Subject (or the subject's legally authorized representative) must be fully informed of the study contents and is able to provide written ICF prior to any study-specific procedures, and is willing to follow the treatment regimen and visit schedule.

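### Protocol 8.9 requires pregnancy reporting only for pregnancies beginning by 28 days after last dose, although contraception runs for 3 months; the last 61 to 64 days carry no duty to report the pregnancy itself (low severity)

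*Protocol*

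**What the plan says.** Protocol 8.9 sets the pregnancy-reporting duty in two parallel paragraphs. For female subjects it covers pregnancies that begin "from the time of signing informed consent to 28 days after the last dose of study drug". For spouses of male subjects it covers those that begin "from the time the male subject signs the informed consent to 28 days after the last dose of study drug". Within that window the site completes a Pregnancy Report Form on the SAE timetable, tells the sponsor, makes an eCRF entry and follows the pregnancy to 30 days after delivery, or to its end if there is no delivery.

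The same section has notification sentences. During the study period, "female subjects should discontinue the study drug as soon as they become pregnant and notify the investigator". For men, "Spouses of male subjects should notify the investigator as soon as they become pregnant during" the study period. It also lists outcomes to be recorded as SAEs, beginning "Any occurrence during pregnancy of: spontaneous or induced abortion, birth defects or congenital malformations in the newborn"; those sentences do not restate the 28-day limit.

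The precaution period in Protocol 3.1 is longer. Criterion 8 asks women of childbearing potential to use two forms of "contraception during the course of the study and for 3 months after their last dose of study drug". Under criterion 9, sexually active men whose partners could conceive "must agree to use 2 recognized methods of contraception during the treatment period and for 3 months after the last dose of study drug". Section 1.3 gives the background: "BN101/belumosudil demonstrated embryo-fetal toxicity/teratogenicity as well as reduced male fertility". It adds that the male findings generally arose above clinically relevant exposures.

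**The concern.** The sponsor treats three months after last dose as a period in which conception should be avoided, but asks to hear of a failed precaution only if it occurs in the first 28 days. For a drug with an animal teratogenicity signal, a conception later in that period is information that a sponsor would normally want, whatever its outcome.

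If only adverse outcomes are reported, through the SAE route, the sponsor sees cases without the normal pregnancies that would put them in proportion. In a 30-subject study any such pregnancy is rare and cannot be recovered once missed.

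**Working it through.** The plan states no figure for this gap, so there is none to reproduce. The check has three parts.

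**1. Length of the gap.** Inputs: 28 days (8.9) and 3 months (3.1, criteria 8 and 9). Three calendar months last 89 to 92 days, depending on the start date.

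- Gap = length of 3 months − 28: 89 − 28 = 61 days; 92 − 28 = 64 days.
- Share of the post-dose contraception period: 61/89 = 68.5%; 64/92 = 69.6%. This is a share of calendar days, not of risk.
- If the ±7-day visit window of section 4.3.5 were read into 8.9 (day 35), the gap would be 54 to 57 days. Section 8.9 states 28 days with no window, so 61 to 64 is the figure to use.
- Ceiling on person-time, assuming that all 30 subjects stop drug and are alive through 3 months: 30 × 61/365.25 = 5.0 person-years; 30 × 64/365.25 = 5.3 person-years. The relevant amount is smaller, since only women of childbearing potential and men with such partners count. The documents do not give that mix, so no expected number of pregnancies can be computed.

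**2. Does another section close the gap?**

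- *Testing:* the last scheduled pregnancy test is at the 28-day visit (4.3.5, Appendix 1).
- *Calls:* the roughly 12-weekly calls in 4.3.6 cover survival, cGVHD treatment and antitumor therapy. Pregnancy is not listed.
- *Appendix 1, note 11:* follow-up to 30 days after delivery is triggered by a positive urine test, but the testing is placed during study treatment.
- *SAE route:* congenital anomaly is an SAE criterion, explained by reference to exposure of either parent (8.6.1.4). Treatment-related AEs and SAEs remain reportable beyond the 28-day window (8.6.2.1). An event counts as related wherever a link cannot be ruled out (8.6.1.3), and an undeterminable relationship is classed as related (8.6.1.5). SAEs after the end of follow-up go to the sponsor (8.11).

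The SAE route therefore catches most adverse outcomes that a site learns of. It does not cover the pregnancy itself, and nothing prompts the site to ask.

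**3. Is drug still present after day 28?** Inputs: half-lives at 200 mg in Table 2 of section 1.5 (median 10.35 h, maximum 48.01 h). Exclusion criterion 18 uses the longer of 28 days and 5 half-lives as its washout.

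- 5 half-lives: 5 × 10.35 = 51.8 h = 2.2 days at the median; 5 × 48.01 = 240 h = 10.0 days at the maximum.
- Half-lives elapsed by day 28 (672 h): 672/10.35 = 64.9 at the median; 672/48.01 = 14.0 at the maximum.

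These are single-dose values from 8 healthy volunteers, so patient values may differ. The margin is nevertheless wide.

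**The case against.** The strongest defence is that contraception is prevention with a margin, whereas reporting follows exposure. Day 28 is the protocol's usual safety horizon, used for all-cause AEs (8.6.2.1) and deaths (8.7.2), and the drug should be gone well before it. Nothing in the documents requires the two windows to match. All of this stands, and it is why the point is low in severity. It does not remove the case for alignment, because the same clearance argument applies to the 3-month contraception rule, which the sponsor kept.

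The notification sentences may also reach further than day 28. The spouse paragraph of 8.9 ends the study period at 28 days, but 8.7.1 uses the same term to include survival follow-up, and the female notification sentence carries no limit of its own. A longer duty to notify is arguable for women. It would not extend the report-form duty. The consent form is not among the documents reviewed, so subjects may be told more there.

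A reader might infer several stronger claims that the documents do not support:

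- *The windows contradict each other.* They do not; a site can comply with both.
- *Late pregnancies carry no reporting duty of any kind.* Adverse outcomes known to the site are largely covered by the SAE route.
- *Pregnancies recognised after day 28 are lost.* Those that began by day 28 are within 8.9, whenever they are recognised.

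**Conclusion.** The point holds as a cheap, optional improvement to safety ascertainment. For 61 to 64 days of the sponsor's own precaution period, a pregnancy in a subject or spouse triggers no report form and no systematic follow-up. What is lost is mainly normal-outcome pregnancies and active detection.

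No harm is demonstrated. Exposure after day 28 is very unlikely, and the number of affected pregnancies may be zero. The 5.0 to 5.3 person-years is a ceiling that rests on all 30 subjects counting, which they will not. The ORR analysis, the sample size and the other analyses in the SAP are unaffected.

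**What to change.** In both the female-subject and the spouse paragraphs of 8.9, change the end of the window from 28 days to 3 months after the last dose of study drug. At the end-of-treatment or 28-day visit, instruct subjects to tell the site of any pregnancy, their own or a spouse's, that begins in that period. This reduces the uncovered interval from 61 to 64 days to zero on paper and needs no new visit or test. Detection would still depend on subjects coming forward.

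A pregnancy question could be added to the 4.3.6 calls, but its reach is limited. The calls apply only to subjects who stop before the end of the main study, and they cease when it ends. If counted from last dose, a call at 12 weeks (day 84) also falls 5 to 8 days short of 3 months.

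The cost is a written amendment with ethics approval (11.6), a possible consent-form update (11.5), and follow-up to 30 days after delivery for any added pregnancy, possibly after the main study has ended. The change could be bundled with the next amendment.

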8.10 Overdose

An overdose dose of BN101/belumosudil has not been determined. Overdose in this study is defined as the intentional or unintentional ingestion of more than the dose to which each subject was assigned according to the study protocol. For the purposes of this study, drug overdoses without clinical signs or symptoms will not be considered AEs. drug overdose-induced AEs will be documented on the AE page of the eCRF in accordance with Section 8.6.2.1 (Collection and Reporting of AEs). SAEs due to drug overdose will be reported according to the procedures described in Section 8.6.2.2 (Collection and Reporting of SAEs).

There are no known specific antidotes for study drug overdose. If an overdose is suspected, supportive therapy should be given based on the subject's clinical condition.

8.11 Rapid Reporting of Suspected Unexpected Serious Adverse Reaction by the Sponsor

Sponsors are required to report Suspected Unexpected Serious Adverse Reactions (SUSARs) to the appropriate authorities on an expedited basis as an Individual Case Safety Report (ICSR) in accordance with the latest applicable regulations. The investigator should sign and read the relevant safety information of the clinical trial provided by the sponsor in a timely manner upon receipt and consider the subject's treatment, whether to adjust it accordingly, communicate with the subject as early as possible if necessary, and should report suspected unexpected serious adverse reactions provided by the sponsor to the ethics committee.

The content of the ICSR should be reported in accordance with the requirements of the ICH 《E2B(R3): Management of Clinical Safety Data: Data Elements for the Transmission of ICSR》. The terminology should be coded using ICH 《M1: MedDRA》.SUSAR is defined as all unanticipated and serious adverse reactions occurring during a clinical trial that are definitely related to or suspected to be related to the test drug.

An unexpected adverse reaction is an adverse reaction whose nature, severity, consequences, or frequency are different from the expected risks described in current information about the test drug (e.g., documents such as the investigator's brochure). The investigator's brochure serves as the primary document that provides the safety reference information used to determine whether an adverse reaction is expected or unexpected. Refer to Section 8.6 of this protocol for the determination of whether it is a

SAE and the determination of causality. For SUSAR, expedited reporting should also be performed when the sponsor and investigator cannot agree on the AE and drug causality determination, and either party determines that a relationship to the test drug cannot be ruled out.

SAEs occurring at the end of the clinical trial or after the end of follow-up until the conclusion of the review and approval is obtained should be reported by the investigator to the sponsor, and should also be subject to expedited reporting if they are unexpected serious adverse reactions. Other situations where rapid reporting is required are:

- 1) For known, serious adverse reactions with an increased incidence judged to be clinically important;
- 2) where there is a clear hazard to the exposed population, e.g. where the drug is ineffective in the treatment of a life-threatening condition;
- 3) Significant safety findings (e.g., carcinogenicity) in newly completed animal testing;
- 4) information obtained by the sponsor from other sources about unexpected serious adverse reactions and other potentially serious safety risks associated with the investigational drug;
- 5) When the sponsor and investigator cannot agree in the determination of causality between the AE and the drug, and in the judgment of either one of them, a correlation with the study drug cannot be ruled out.

The following conditions are generally excluded from expedited reporting:

- 1) Non-SAE;
- 2) SAE not related to the test drug;
- 3) Serious but expected adverse reactions;

Please refer to the Standards and Procedures for Rapid Reporting of Safety Data During Drug Clinical Trials for specific reporting procedures.

SUSAR Rapid Reporting Timeframe:

- 1) For fatal or life-threatening SUSARs, sponsors should report as soon as possible, but no later than 7 days after first notification, and report, and complete follow-up information within the next 8 days. [Note: The day the sponsor is first notified is Day 0.]
- 2) For non-fatal or life-threatening SUSARs, the sponsor shall report as soon as possible, but not more than 15 days, after initial notification.

[figure not shown]
After the initial report, the sponsor should continue to follow up and report new information or changes to the previous report, etc., in a timely manner in the form of a follow-up report, with a reporting time limit of 15 days from the date the new information is obtained.

9. Data Managment

9.1 Data Management workflow

The study data management is the responsibility of the CRO Data Department to ensure the authenticity, integrity, privacy and traceability of clinical trial data.

9.1.1 Workflow

9.1.2 Role and Responsibility

EDC Role	Responsibility				
	1) Data Entry				
Clinical Research Coordinator (CRC)	2) Add comments				
(ene)	3) Answer Query				
	1) Data Entry				
Sub Investigator (Sub-I)	2) Add comments				
Sub investigator (Sub-1)	3) Answer query				
	4) Electronic signature				
	1) Data Entry				
Principal Investigator (PI)	2) Add comments				
Finicipal investigator (F1)	3) Answer query				
	4) Electronic signature				
Clinical Research Associate	1) Source data consistency check				
(CRA)	2) Send query				
Medical Monitor (MM)	1) Send query				
	1) Send query				
Data Management (DM)	2) Answer query				
	3) Freeze and Unfreeze data				

EDC Role	Responsibility
Read-only	1) Read-only
Safty	1) Send query
Coder	1) Send query

